15.2.3.10. Effort Expenditure for Reward Task

Each outcome measure of the EEfRT will be summarized (mean, standard deviation, median, and

---

Document:	C:\Users\q718413\Documents\NEP-MDD-201_SAP_v1.0_Final_06Dec2018.docx		
Author:	[name]	Version Number:	1.0
		Version Date:	06Dec2018

Template No: CS\_TP\_BS016 Revision 4  
Effective Date: 01Apr2016

Reference: CS\_WI\_BS005

Analysis Plan

---

range) by treatment group at each visit. Line plots of means (+/-SD) will also be presented by treatment group and visit.

The analysis of completion rates will use an ANOVA model with a term for treatment to analyze treatment differences at each scheduled visit. The models LS Means and standard errors (SEs) will be presented for each treatment group. The difference in LS Means with corresponding SEs, 95% confidence intervals for differences, and p-values will also be presented. No adjustments will be made for multiple comparisons.

The analysis of preference will be completed utilizing Generalized Estimating Equation (GEE) models. A binary logistic distribution will be used to model the dichotomous outcome of preference at each scheduled visit. At each visit a series of models using a variety of factors will be fit. All models in the series will include explanatory variables reward magnitude, reward probability, and expected value (reward magnitude X probability) as a base. For each series, four models will be fit. The first will include the base variables with the additional variable of interest with no interactions. The next three models will include the same but with an interaction term between the variable of interest and each base variable in order. The variables of interest that will be explored include:

- Age
- Sex
- Treatment
- MADRS Total Score
- SHAPS Score (0 – 14 scoring method)
- DARS Total Score

The parameter estimates, standard error, 95% confidence interval, degrees of freedom and p-values will be presented to for each model.

All data will be listed by treatment and patient.

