#### 9.5 VISIT 5, WEEK 4 (DAY 29)

The following order of procedures is recommended to prioritize safety and efficacy assessments:

1. The Investigator will conduct/administer the following assessments (\*or by his/her designee where asterisked):
  - a. Weight\*
  - b. Investigator-administered MADRS followed by the computer-administered MADRS
  - c. Allow patient to complete HADS, SHAPS, DARS, and pain question; reviewed by site personnel qualified to oversee completeness\*
  - d. HAM-A
  - e. C-SSRS
  - f. CGI-I
  - g. SHSF and if applicable, SHFU
  - h. Concomitant therapies review\*
  - i. Adverse events review
  - j. Neurological examination
  - k. Vital signs (BP and pulse both supine and standing, respiratory rate,

temperature)\*

1. 12-lead ECG\*
2. Blood and urine collection for central laboratory analysis (including urine pregnancy test for women of child-bearing potential)
3. The patient-returned investigational study drug will be accounted for and patient will be re-instructed if found to be out of compliance
4. Complete IWRS
5. The rater will administer the PRT and EEfRT in the order assigned by IWRS
6. Collect and/or monitor digital assessments, as applicable
7. Collect three blood samples for pharmacokinetic analysis at the following time points: (1) prior to dosing, (2) between 15 min and 2 hours after dosing, and (3) between 4 and 8 hours after dosing
8. After completing all study procedures including the pre-dose pharmacokinetic blood sample, the patient will take their dose of investigational study drug from the bottle dispensed at this visit with a light snack at the site
9. Dispense allocated study drug and instruct patient on the importance of compliance and returning the dispensed bottle(s) with any unused study drug at each visit.
10. Instruct all patients to take their assigned study drug dose daily, **and not take study drug the day of their next clinic visit.**

The Investigator will review the results of the central laboratory tests for safety prior to the next visit.

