8. Proportion of patients who demonstrate significant clinical improvement, where **improvement** is defined by a score of 1 (very much improved) or 2 (much improved) on the CGI-I at Week 8.

The following secondary efficacy endpoints based on the performance tasks will be analyzed and presented in summary and graphical displays.

Data for the FERT will be summarized (mean, standard deviation, range) for each treatment group at each visit. All treatment differences will be estimated with 95% CI. No adjustments will be made for multiple comparisons. The analysis will employ ANOVA models without adjusting for covariates. However, if significant confounds are identified, a secondary analysis will be performed to examine the relationship between FERT outcome measures and other covariates. A full description of the statistical analysis methods for FERT outcome measures will be provided in in the SAP.

9. Outcome measures from the FERT
  - a) Accuracy
  - b) Misclassification
  - c) Average reaction time
  - d) Target sensitivity
  - e) Response bias

Data for all PRT outcome measures will be summarized (mean, standard deviation, range) for each treatment group at each visit. The ANOVA models will be used to compare between treatment groups. For “Response bias” and “Discriminability,” treatment group, block, and treatment-by-block interactions will be considered fixed effects. For “Reaction time” and “Hit rates,” the stimulus type will be included as an additional fixed effect. The details of the analysis methods for these outcome measures will be described in the SAP.

10. Outcome measures from the PRT

- a) Response bias
- b) Discriminability
- c) Reaction time
- d) Hit rates

Data for all EEfRT outcome measures will be summarized (mean, standard deviation, range) for each treatment group at each visit. Statistical analyses of the Preference during the EEfRT trial will be performed using Generalized Estimating Equation (GEE) models. A binary logistic distribution will be used to model the probability of the Preference. The relationship and interactions between Preference and independent variables of reward magnitude, reward probability, expected value, age, sex, and efficacy parameters will be explored. The ANOVA model will be used to compare the completion rates between treatment groups. The details of the analysis method for these outcome measures will be described in the SAP.

11. Outcome measures from the EEfRT

- a) Preference (hard or easy task choice)

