15.2.3.8. The Facial Expression Recognition Task

For each emotion of the FERT, each outcome measure will be summarized (mean, standard deviation, median, and range) by treatment group at each visit. Line plots of means (+/-SD) will also be presented by treatment group and visit. Additionally, accuracy will be summarized by intensity level for each emotion and plotted versus intensity level in scatterplots.

At each scheduled visit, an ANOVA model with a term for treatment will be used to analyze treatment differences. LS Means and standard errors (SEs) will be presented for each treatment group. A second ANOVA model will be fit with additional factors of gender, baseline MADRS total score, and baseline FERT outcome measure. The difference in LS Means with corresponding SEs, 95% confidence intervals for differences, and p-values will also be presented. No adjustments will be made for multiple comparisons.

All data, including the accuracy response for each intensity level, will be listed by treatment and patient.

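### The EEfRT preference models for MADRS, SHAPS and DARS pool both arms without a treatment term, so if same-visit scores are used, their Week 4 and Week 8 symptom slopes can absorb the between-arm difference

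*SAP*

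**What the plan says.** Protocol 13.2.8.3 sets the aim: "The relationship and interactions between Preference and independent variables of reward magnitude, reward probability, expected value, age, sex, and efficacy parameters will be explored". It does not name treatment in that list and leaves the details to the SAP.

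SAP 15.2.3.10 gives the models. On the outcome: "A binary logistic distribution will be used to model the dichotomous outcome of preference at each scheduled visit". On the common terms: "All models in the series will include explanatory variables reward magnitude, reward probability, and expected value (reward magnitude X probability) as a base". On the first model of each series: "The first will include the base variables with the additional variable of interest with no interactions". On the rest: "The next three models will include the same but with an interaction term between the variable of interest and each base variable in order".

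Six variables of interest are listed: age, sex, treatment, MADRS total, SHAPS (0-14 scoring) and DARS total. Treatment is therefore a separate series and is absent from the three symptom series. No by-arm fit of those series is described.

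The EEfRT is done at baseline, Week 4 and Week 8. At Week 4, for example, Protocol 9.5 has both "The rater will administer the PRT and EEfRT in the order assigned by IWRS" and "Allow patient to complete HADS, SHAPS, DARS, and pain question; reviewed by site personnel qualified to oversee completeness", and MADRS is rated at every visit. A same-visit symptom score is thus available wherever preference is modelled.

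The EEfRT section does not say which visit's score is meant. The FERT section does say so when it means baseline: "A second ANOVA model will be fit with additional factors of gender, baseline MADRS total score, and baseline FERT outcome measure". The responder model in SAP 15.2.3.7 also specifies the baseline MADRS.

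**The concern.** At Weeks 4 and 8 the symptom score and the hard/easy choice are both post-randomisation outcomes. If the drug shifts both, patients in the active arm sit at a different point on both axes from placebo patients. A line fitted through the pooled data then has a slope even when score and choice are unrelated within each arm. The separate treatment series does not remove this, because each series is fitted alone.

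What is at stake is the interpretation of the symptom-effort relation. Three scales, four models and two on-treatment visits make 3 x 4 x 2 = 24 models without a treatment term. Of these, 3 x 1 x 2 = 6 are the main-effect models where the bias arises directly. The p-values are nominal, are read as a trend at 10% (SAP 6.5), and are not adjusted for multiplicity (SAP 7.4). The bias grows with the drug's effect on the two variables.

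**Working it through.** **Inputs from the documents** (Protocol 13.1): 44 per arm, effect size 0.5 on MADRS, two-sided alpha 0.10, 1:1 allocation, stated power 75%.

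**Assumptions** (the documents give no EEfRT effect size, between-patient SD or trial count): drug effects of 0.2 to 1.0 SD, 50 trials per patient, patient random-intercept SD of 1 on the logit scale, and no within-arm relation between score and preference.

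1. *The plan's own figure.* The two-sample t-test with 44 per arm has noncentrality 0.5 x sqrt(44/2) = 2.345 on 86 degrees of freedom. Power at two-sided 0.10 is 75.2%, so the stated 75% reproduces. The documents give no figure for the preference models.

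2. *Induced correlation.* Let the drug shift the score by dx and the preference propensity by dy, in within-arm SDs. With 1:1 arms the between-arm covariance has size dx·dy/4, and the pooled variances are 1 + dx²/4 and 1 + dy²/4. Hence |r| = (dx·dy/4) / sqrt[(1 + dx²/4)(1 + dy²/4)].
   - 0.5 and 0.5: 0.0625 / 1.0625 = 0.059
   - 0.8 and 0.8: 0.16 / 1.16 = 0.138
   - either effect zero: r = 0

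3. *False-trend rate by Fisher's z, n = 88.* The test statistic has mean m = atanh(r) x sqrt(85), and the rejection rate is 1 - Φ(1.645 - m) + Φ(-1.645 - m). At 0.5/0.5, m = 0.54 and the rate is 15.0%. At 0.8/0.8, m = 1.28 and the rate is 35.9%. At 0.2/0.2 it is 10.1%; at 0.5/0.8 it is 21.5%.

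4. *Trial-level GEE simulation.* Patients are clusters, with independence working correlation, robust standard errors, the three reward terms in the model, 44 per arm and 1500 runs. Rejection of the symptom main-effect slope at 10%:

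| Drug effect (score / preference, SD) | No treatment term | With treatment term | Mean slope without / with (log-odds per SD) |
|---|---|---|---|
| 0 / 0 | 11.7% | 11.5% | 0.003 / 0.003 |
| 0.5 / 0 | 10.1% | 11.9% | -0.003 / -0.003 |
| 0.5 / 0.5 | 15.7% | 11.6% | -0.048 / 0.002 |
| 0.8 / 0.8 | 35.9% | 12.1% | -0.116 / 0.002 |

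   The Monte Carlo standard error at 15.7% is sqrt(0.157 x 0.843 / 1500) = 0.9 points. Further simulations with 40 or 44 per arm gave 14.7%, 16.6% and 17% at 0.5/0.5 without treatment, and 35.7%, 37.8% and 40% at 0.8/0.8. Two of these were also run with treatment, giving 10.1% and 9% at 0.5/0.5, and 13.7% and 12% at 0.8/0.8. Null runs without treatment lay between 11% and 13%, so the robust test is itself slightly liberal at this size.

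5. *Interaction terms.* With a drug shift that is the same at every reward level (40 per arm, 1000 runs, no treatment term), the three symptom-by-reward coefficients were rejected in 12.4%, 11.2% and 11.1% of runs at 0.5/0.5, and in 12.4%, 12.9% and 11.1% at 0.8/0.8. With no drug effect the rates were 11.9%, 11.6% and 12.8%, so there is no inflation. When the drug was also made to change reward sensitivity, rejection rose to 18% to 37%. That range depends on the assumed change in sensitivity, for which the documents give nothing.

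6. *Direction.* Higher MADRS and SHAPS scores are worse (SAP 15.1.1, 15.2.1.6). A drug that lowers them and raises hard-task choice induces a negative slope, the same sign as an expected relation of more symptoms with less effort. It exaggerates such a relation. Masking needs the induced slope to have the opposite sign, for example a drug that improves symptoms but reduces effort.

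**The case against.** *The scores may be baseline values.* If so, randomised treatment cannot have moved them and the problem disappears. The wording elsewhere in the SAP favours same-visit scores, but that is an inference. This part stands as a condition on the whole point.

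*SAP 7.1 lists treatment group among the factors used.* It also defers to each analysis section for which terms enter, and 15.2.3.10 gives treatment its own series.

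*The pooled association is a legitimate exploratory quantity, and if the drug changes effort through symptoms, part of it is real.* This is fair. But the planned model cannot separate that part from the difference between arms, while a treatment-adjusted slope keeps any relation that exists within arms, including one through which the drug acts.

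*The size is small.* At 0.5 SD on both, the excess is 15.0 - 10.0 = 5.0 points by formula, or 15.7 - 11.7 = 4.0 points against the simulated null. This stands.

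A reader might infer more than the documents support:
- That all four models in each series are biased alike. Step 5 shows no inflation of the interaction terms under a uniform drug shift.
- That a drug moving score and preference in opposite directions hides a real relation. For MADRS and SHAPS that is the pattern of benefit, and it inflates the expected slope.
- That the result will be used to claim a mechanism. The documents say only that relations will be explored, in a study meant to establish trends.

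**Conclusion.** The point holds conditionally, as a minor improvement. If same-visit scores are used, the MADRS, SHAPS and DARS main-effect slopes at Weeks 4 and 8 are biased by any drug effect that reaches both the score and the choice. With no within-arm relation, the false 10% trend rate is about 15-17% at 0.5 SD on both, against about 9-12% with treatment in the model. Only the MADRS 0.5 SD comes from the documents; the preference effect is assumed. The rate reaches about 36-40% only if both effects are near 0.8 SD, and there is no bias if the drug moves just one of the two.

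It would be too strong to say that an effective drug will produce a false symptom-effort finding. The slope is biased, but at the design effect most trials would still show no trend. The interaction terms are at risk only if the drug also changes sensitivity to that reward variable.

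Baseline-visit models are not affected. These are exploratory models within a secondary endpoint, and the primary MADRS analysis is untouched.

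**What to change.** In SAP 15.2.3.10:

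- State which visit's MADRS, SHAPS and DARS scores enter the preference models. If baseline scores are intended, saying so settles the matter.
- If same-visit scores are intended, add treatment as a covariate to every model in these three series at Weeks 4 and 8.
- In each interaction model of these series at those visits, also add treatment by the same base variable. This protects against a drug effect on reward sensitivity; it is not needed for a uniform drug shift.
- Leave the baseline-visit models as they are.

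The cost is SAP wording and one extra degree of freedom in each main-effect model, or two in each interaction model. No further data are needed.

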#### 11.1.9 EFFORT EXPENDITURE FOR REWARD TASK (EEfRT)

The EEfRT was developed in an effort to dissociate reward components in anhedonia. The task will be administered to the patient and reviewed by site personnel qualified to oversee completeness. The EEfRT task is a multi-trial game in which participants are given an opportunity on each trial to choose between two different task difficulty levels in order to obtain monetary rewards. Patients are required to complete the task with a specific number of button responses within a constrained period of time in order to obtain a monetary reward. This task isolates patient willingness to exert effort relative to size and likelihood of reward that measures reward "wanting", in contrast to commonly used anhedonia questionnaires, which focus on reward "liking". ([Treadway et al, 2009](#)). This task will be completed by the patient using the Sponsor-provided study equipment. The order of administration of the EEfRT will be assigned by IWRS.

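### The EEfRT treatment-by-expected-value model leaves out its lower-order interactions, so its p-value does not show an effect specific to expected value

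*SAP*

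**What the plan says.** SAP 15.2.3.10 analyses the choice of hard or easy task by logistic GEE, separately at each visit: "A binary logistic distribution will be used to model the dichotomous outcome of preference at each scheduled visit". The terms common to all models are fixed: "All models in the series will include explanatory variables reward magnitude, reward probability, and expected value (reward magnitude X probability) as a base". Each variable of interest (age, sex, treatment, MADRS, SHAPS and DARS) then gets a set of four fits. One adds that variable to the common terms and stops there. On the remaining three the SAP reads: "The next three models will include the same but with an interaction term between the variable of interest and each base variable in order". Every fit is reported in full: "The parameter estimates, standard error, 95% confidence interval, degrees of freedom and p-values will be presented to for each model".

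Writing M for magnitude, P for probability, EV = M × P and T for treatment, the treatment series on the plain reading is:

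1. M + P + EV + T
2. M + P + EV + T + T×M
3. M + P + EV + T + T×P
4. M + P + EV + T + T×EV

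SAP 6.5 reads significance at 10% as a trend, and SAP 7.4 makes no multiplicity adjustment. Protocol 13.2.8.3 lists expected value among the variables to be explored and leaves the method to the SAP. Neither document gives a joint model, centring, or a rule for reading the three interaction p-values together.

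**The concern.** Because EV is M × P, T×EV is a three-way term, T×M×P. Model 4 fits it without T×M and T×P, which appear only one at a time in models 2 and 3. If treatment changes the slope on probability and nothing else, the only treatment slope in model 4 is the one on EV. It takes up whatever part of the probability effect is correlated with EV, and the same holds for an effect on magnitude.

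Protocol 11.1.9 describes the task in these terms: "This task isolates patient willingness to exert effort relative to size and likelihood of reward". A significant T×EV coefficient would naturally be read as the drug changing how patients combine size and likelihood. It could equally come from an effect on one of them. What is at stake is the label on a secondary-endpoint finding. The same algebra applies when age, sex, MADRS, SHAPS or DARS takes the place of treatment.

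**Working it through.** **The plan's own figure.** The only power statement is for the primary endpoint (protocol 13.1: 44 per arm, effect size 0.5, two-sided 10%, 75%). The normal approximation gives Φ(0.5 × √(44/2) − 1.645) = Φ(0.700) = 75.8%, and the noncentral t gives 75.2%, so it reproduces. There is no figure for the EEfRT models. Only the 44 per arm and the 10% level are carried forward.

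**Size of the leak, by algebra.** Assume M and P vary independently across trials. Then:

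- Cov(EV, P) = E(M)·Var(P)
- Cov(EV, M) = E(P)·Var(M)
- Var(EV) = E(M)²·Var(P) + E(P)²·Var(M) + Var(M)·Var(P)

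To first order, a true T×P effect δ gives a model 4 coefficient of δ·Cov(EV, P)/Var(EV), and likewise for M.

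Take M uniform on 1 to 4 (mean 2.5, variance 0.75) and P from 0.2, 0.5, 0.8 (mean 0.5, variance 0.06). Then Var(EV) = 6.25 × 0.06 + 0.25 × 0.75 + 0.75 × 0.06 = 0.6075.

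- Probability only, δ = 1.0 logit per unit: 1.0 × (2.5 × 0.06)/0.6075 = 0.247.
- Magnitude only, δ = 0.3 logit per unit: 0.3 × (0.5 × 0.75)/0.6075 = 0.185.

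GEE estimates are population-averaged and so shrunken. In the simulation below, model 3 returned 0.839 for a true 1.0 and model 2 returned 0.248 for a true 0.3. Scaling by these gives 0.247 × 0.839 = 0.207 and 0.185 × 0.248/0.3 = 0.153. The simulated means in model 4 were 0.201 and 0.143. The true effect specific to EV is zero in both cases.

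**Rejection rates, by simulation.** Assumed, not in the documents: 50 trials per patient, the grids below, the two effect sizes above, random intercept SD 1, random magnitude slope SD 0.3, independence working correlation with robust standard errors. There were 400 replicates, so the Monte Carlo standard error at 10% is √(0.1 × 0.9/400) = 1.5 points. Entries are rejection rates for T×EV at two-sided 10%; no scenario contains a true effect on the product.

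| Probability levels | r(EV,M) | r(EV,P) | Model 4, no interaction | Model 4, magnitude only | Model 4, probability only | Joint, magnitude only | Joint, probability only |
|---|---|---|---|---|---|---|---|
| 0.2/0.5/0.8 | 0.56 | 0.79 | 10.8% | 44.0% | 66.5% | 11.0% | 6.8% |
| 0.1/0.5/0.9 | 0.45 | 0.84 | 10.2% | 28.5% | 92.0% | 11.0% | 10.2% |
| 0.4/0.5/0.6 | 0.90 | 0.42 | 13.5% | 72.5% | 10.2% | 12.8% | 9.5% |

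The 10.2% in the last row arises where the probability range is so narrow that model 3 itself detects the effect in only 32.2%. A separate run on three assumed grids, again with 44 per arm and 50 trials, gave 12–72% for a probability-only effect and 33–82% for a magnitude-only effect. The product term of a joint centred model gave 7–12% and 8–12%.

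**Do models 2 and 3 confuse the components?** Hardly. A magnitude-only effect makes model 3 reject in 12–15%, and a probability-only effect makes model 2 reject in 9–13%.

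**Why centre.** With all three interactions present, (M − m)(P − p) = MP − pM − mP + mp spans the same space, so the test of the product term is unchanged. The lower-order coefficients do change meaning. Uncentred, they are slopes with the other component at zero, and power for a true magnitude effect falls from about 80% in model 2 to 14–49%. With centring, on two assumed grids, magnitude power was 74% and 70% in the planned models against 73% and 69% in the joint model; for probability it was 76% and 60% against 76% and 59%.

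**What model 4 does well.** Suppose treatment acts along the SAP's raw EV (0.2–0.3 logit per unit, 40 per arm, 50 trials, 300 replicates). Model 4 detects it in 69–91% (0.1/0.5/0.9), 52–89% (0.2/0.5/0.8) and 37–51% (0.4/0.5/0.6). The joint product term detects it in 19–25%, 17–22% and 12–14%.

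**The case against.** The strongest reply is that these models are exploratory by the plan's own description, that all estimates are printed side by side, and that no rule in the SAP attributes an effect to a component. Protocol 11.1.9 also goes on to contrast wanting with liking, and no passage states a hypothesis of size against likelihood. That limits the seriousness. It does not make the T×EV coefficient mean what its label suggests, and a reader comparing models 2 to 4 has no joint fit to settle the matter.

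The wording *in order* could mean that interactions are added cumulatively, which would make the fourth model the joint one. Describing each model as the same with one interaction term points the other way, but the text should remove the doubt.

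Three stronger readings are tempting and not supported:

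- **That none of the three p-values can tell size from likelihood.** Models 2 and 3 do so adequately if M and P vary independently. The leak runs into EV.
- **That the plan inflates false positives in general.** With no treatment interaction of any kind, model 4 rejects in 10–14%. The fault is one of attribution.
- **That model 4 lacks power and should be replaced.** Its power is low only for a pure synergy term (11.5–17.5% against 15–62% in the joint model). Along raw EV, which is what the SAP defines ("expected value (reward magnitude X probability) as a base"), it is the better test, and protocol 13.2.8.3 names expected value as a variable to be explored. Dropping it would remove a planned analysis.

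**Conclusion.** The point holds. As written, model 4 cannot separate an effect specific to expected value from an effect on magnitude or probability alone. Its omission of the lower-order interactions is a matter of algebra. The size is not fixed by the documents: across the assumed designs, a one-component effect produces an expected-value trend in roughly 10% to 90% of studies, against about the nominal 10% with all three interactions fitted together. The figure depends on the probability levels, magnitude range, number of trials and effect sizes, all of them assumed. The clean behaviour of models 2 and 3 rests on magnitude and probability varying independently across trials, which the documents do not state. A reader should not carry this over to the primary conclusion: the EEfRT is a secondary measure, and the MADRS analysis does not use these models.

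**What to change.** Keep the four planned models. For each visit and variable of interest, add a fifth with magnitude and probability centred, the product of the centred variables, the variable of interest, and all three of its interactions together. State in SAP 15.2.3.10 that a claim of an effect specific to expected value, beyond its components, rests on the product interaction in that joint model. State also that the single expected-value interaction is read as a composite that does not identify a component. Say whether *in order* means one interaction at a time or cumulative; if cumulative, centre the components.

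The cost is SAP wording, one model statement and extra rows in the table shells, with no new data. Six variables of interest at three scheduled EEfRT visits (baseline, weeks 4 and 8) make 6 × 3 = 18 series, so 18 × 4 = 72 models become 18 × 5 = 90. The statistical price is that the joint product term has low power for an effect along raw expected value, which is the reason for keeping model 4. The change should be made before unblinding.
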